## 6.2.2 Secondary outcome analysis

Summary statistics by treatment arm will be computed for EQ-5D-5L, pain, PROMIS, self-efficacy, exercise adherence and complications. Similar methods to the primary outcome will be used to analyse continuous secondary outcomes, with their mean and standard deviation or median and interquartile range reported. Only the intention to treat (ITT) population will be used for secondary outcome analysis (see table 10 in AFTER\_SAP\_DDT\_V1.0\_18Aug2022).

OMAS at baseline, 2 and 4 months: The treatment difference for the OMAS at other follow-up time points will be the adjusted difference at these time points taken from the same model used for the primary outcome analysis.

EQ-5D-5L utility score (at baseline, 2,4 and 6 months): will be calculated by the ED-5D-5L mapping function (17) and range from -0.594 to 1. If a participant dies before end of follow-up, their utility score will be imputed as 0. Similar to the analysis for primary outcome, a mixed effect model with recruitment centre as random effect and adjust for stratification factor (initial fracture management) and baseline utility score. The independent variable of the model will be treatment and follow-up time point interaction. This model will adjust for stratification factors of randomization (recruitment centre and initial fracture management (operative vs non-operative), as well as important prognostic factors of age and sex. Results for treatment effect at each of the follow-up timepoint will be presented with confidence intervals and p-values.

EQ-5D-5L VAS score (at baseline, 2, 4 and 6 months): is a score ranges from 0 to 100, with better score indicating better health. The analysis for the VAS score will be the same as with the EQ-5D-5L utility score, but adjusting for baseline EQ-5D-5L VAS score.

PROMIS Physical Function (at baseline, 4 and 6 months): assesses the physical function of individuals. A normalised score will automatically be calculated by REDCap built-in programmes. Similar to the analysis for the primary outcome, a mixed effect model with recruitment centre as random effect and adjust for stratification factor (initial fracture management) and baseline PROMIS score. The independent variable of the model will be treatment and follow-up time point interaction. This model will adjust for stratification factors of randomization (recruitment centre and initial fracture management (operative vs non-operative), as well as important prognostic factors of age and sex. Participants who have no access to the online PROMIS computer-adaptive test questionnaire can complete a paper-based PROMIS short form. A sensitivity analysis excluding the PROMIS short form will be conducted to assess

the robustness of the analysis. Results for treatment effect at each of the follow-up timepoints will be presented with 95% confidence intervals and p-values.

Pain (at baseline, 2, 4 and 6 months) will be assessed by both the OMAS and EQ-5D-5L subscale. OMAS pain has 5 categories and ranges from 0-25, the pain decreases as score increases. EQ-5D-5L pain has 5 categories and ranges from 1-5, the pain increases as the score decreases. Both scores will be analysed using a mixed ordinal regression model, adjusting for centre as a random effect and fixed effects for fracture management, their respective baseline score, as well as important prognostic factors of age and sex.

Self-efficacy for exercise (SEE) score (at baseline, 4 and 6 months): ranges from 0-90 with 90 being the most confident and 0 being the least confident for conducting exercise. A mixed effect model with recruitment centre as random effect and adjust for stratification factor (initial fracture management) and baseline SEE score, as well as important prognostic factors of age and sex. The independent variable of the model will be treatment and follow-up time point interaction.

Exercise frequency (at 2, 4 and 6 months): records the frequency of exercise that participants perform in a week, ranges from 7 days to less than 1 day a week. Summary statistics by treatment arm will be presented.

Complications: will be reported by participants and verified by sites. Both patient-reported complications (at 2, 4 and 6 months) and site-verified complications (ad-hoc) will be summarised by treatment arm (see table 11 and 13 in AFTER\_SAP\_DDT\_V1.0\_18Aug2022). The number and its associated percentage will be reported for each complication category. A logistic regression model will be used to analyse this outcome variable.

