## 4.3 Measurement of health outcomes

The primary health outcome measure will be QALYs derived from utility scores, obtained using the EQ-5D-5L HRQoL instrument. The EQ-5D-5L instrument facilitates the generation of a utility score from a person's health related quality of life. A utility score refers to the preference that individuals have for any particular set of health outcomes. The EQ-5D-5L's descriptive system consists of five health dimensions (mobility, self-care, usual activity, pain/discomfort, and anxiety/depression) each with five levels of severity to choose from (no problems, slight problems, moderate problems, severe problems, and extreme problems). Although not used to derive utilities, the

EQ-5D-5L HRQoL instrument also contains a visual analogue scale that records the participant's self-rated health from the worst to best health that they can imagine having. Measurement of HRQoL will be recorded using the trial questionnaires at baseline and at two-, four- and six-months post randomization.

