# 2.1 Objectives

**Table 1** Primary and secondary objectives and endpoints.

	Objectives	Outcome Measures	Timepoint(s)
Primary	Ankle Function	Olerud and Molander Ankle Scale (OMAS)	6 months post- randomization
Secondary	Ankle Function	OMAS	Baseline, 2 and 4 months post-randomization
	Health-related quality of life	EQ-5D-5L	Baseline, 2, 4 and 6 months post- randomization
	Pain	Pain sub-scales of the EQ-5D-5L and OMAS	Baseline, 2, 4 and 6 months post- randomization
	Physical Function	PROMIS Physical Function	Baseline, 4 and 6 months post-randomization
	Self-efficacy	Self-Efficacy Exercise Score (SEE)	Baseline, 4 and 6 months post-randomization
	Exercise adherence	Self-reported exercise frequency	2, 4 and 6 months post- randomization
	Complications	Complications Questionnaire and Case Report Form	2, 4 and 6 months post- randomization
	Resource use	Health economics questionnaire	2 and 6 months post- randomization

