## 6.1.2 Secondary outcomes

**Ankle Function:** measured by completion of the Olerud and Molander Ankle Score (OMAS) at baseline, 2 and 4 months after randomization.

Health-related quality of life: assessed using the EuroQol 5 Dimensions (EQ-5D-5L) score (11). The EQ-5D-5L is a validated, generalised and standardised instrument comprising a VAS measuring self-rated health and a health status instrument, consisting of a five-level response (no problems, some problems, moderate problems, severe problems and unable) for five domains related to daily activities; mobility, self-care, usual activities, pain and discomfort, and anxiety and depression. Responses to the health status classification system are converted into an overall score using a published utility algorithm for the UK population. The EQ-5D health status scale ranges from negative scores reflecting a patient's quality of life being worse than death, and 0 [death] to 1 [perfect health]. A respondent's EQ-VAS gives self-rated health on a scale where the endpoints are labelled 'best imaginable health state' (100) and 'worst imaginable health state' (0). This is measured at baseline, 2, 4 and 6 months after randomization.

**Pain:** assessed using the sub-scales of the OMAS and EQ-5D-5L. This is measured at baseline, 2, 4 and 6 months after randomization.

**Physical function**: assessed using PROMIS Physical Function (12). Patient Reported Outcome Measurement Information System (PROMIS) questionnaires are administered electronically, via a Computer Adaptive Test (CAT),

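### SAP section 6.2.2 states the direction of the EQ-5D-5L pain score against the plan's own level order, so the pain effect could be misread

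*SAP*

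**What the plan says.** Pain is a secondary outcome. SAP section 2.1 (Table 1) names its measure as the "Pain sub-scales of the EQ-5D-5L and OMAS", at baseline, 2, 4 and 6 months.

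SAP section 6.2.2 gives the direction of each score in consecutive sentences. For the first, "OMAS pain has 5 categories and ranges from 0-25, the pain decreases as score increases". For the second, "EQ-5D-5L pain has 5 categories and ranges from 1-5, the pain increases as the score decreases". It then sets the model: "Both scores will be analysed using a mixed ordinal regression model, adjusting for centre as a random effect and fixed effects for fracture management", with further adjustment for the respective baseline score, age and sex.

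The response levels are described in two places. SAP section 6.1.2 gives "no problems, some problems, moderate problems, severe problems and unable". Section 4.3 of the Health Economic Analysis Plan (HEAP) gives "no problems, slight problems, moderate problems, severe problems, and extreme problems" and calls them levels of severity. The labels differ slightly, but the order is the same.

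The SAP introduction refers to a companion Data Definitions and Tables document for full outcome definitions, to be read together with the SAP. That document is not shown.

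**The concern.** An ordinal model returns a treatment coefficient whose meaning depends wholly on which end of the scale is the bad one. For the EQ-5D-5L pain item, the sentence in SAP section 6.2.2 is the only explicit guide to this. The section does not say what an odds ratio above or below 1 would mean for either pain score.

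The sentence conflicts with the level order given elsewhere in the same file. It also implies that the two pain scores run in parallel, when on the listed order they run in opposite directions. An analyst or reader who relied on it could take a reduction in pain for an increase. The two pain measures could then seem to disagree when they agree.

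**Working it through.** The plan states no figure on this point, so the check sets the passages side by side and adds a short illustration.

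**1. Direction implied by the sentences in SAP 6.2.2.**
- OMAS pain, 0 to 25: pain falls as the score rises, so a higher score means less pain.
- EQ-5D-5L pain, 1 to 5: pain rises as the score falls, so a higher score means less pain.

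The two sentences differ in wording but state the same direction.

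**2. Direction implied by the level order in SAP 6.1.2 and HEAP 4.3.**

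| Position | SAP 6.1.2 | HEAP 4.3 |
|---|---|---|
| 1 | none | none |
| 2 | some | slight |
| 3 | moderate | moderate |
| 4 | severe | severe |
| 5 | unable | extreme |

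Numbered in this order, 1 is no pain and 5 is the worst, so a higher score means more pain. This is the opposite of step 1. Neither section prints numbers against the labels. The numbering is inferred from the list order and the 1 to 5 range.

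**3. When a misreading arises.**

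| Item as modelled | Coefficient read by | Result |
|---|---|---|
| Listed order (5 = worst) | Response labels | Correct |
| Listed order (5 = worst) | Sentence in 6.2.2 | Direction reversed |
| Reverse-coded (5 = none) | Sentence in 6.2.2 | Correct |

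The sentence is right only if the item is reverse-coded, and neither the SAP nor the HEAP says that it is.

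**4. What changes numerically.** As an illustration, an ordinal logit was fitted to simulated data that do not come from the trial. There were 4,000 people, half in each group, and treatment lowered pain by 0.5 on the latent log-odds scale.
- Coded 1 = none to 5 = extreme: coefficient -0.556, odds ratio exp(-0.556) = 0.57.
- Coded in reverse: coefficient +0.556, odds ratio exp(0.556) = 1.74.

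The odds ratios are reciprocals (1/0.5735 = 1.744). The magnitude is the same and the sign is opposite. This shows only that reversing the scale reverses the sign. It says nothing about the effect to expect in this trial. The exact mirror image holds for a symmetric link such as the logit; SAP 6.2.2 does not name the link.

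**The case against.** The strongest reply is that this is a slip of wording with little practical reach.

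- **The key is inferred.** No number-to-level key is printed, and the Data Definitions and Tables document may supply one. A reverse-coded variable, aligned with OMAS pain, would make the sentence true as written. This stands as a limit on certainty. It does not rescue the text, because a reversal that departs from the listed order needs to be stated.
- **The plan has checks.** SAP 6.2.2 requires pain summaries by arm, so the raw distribution would be visible beside the model result. SAP 5.6 has derived data checked by hand in 15 participants. SAP section 7 has an independent statistician repeat the analyses of key secondary outcomes, EQ-5D-5L among them. These could catch the slip. However, section 7 does not say whether the pain item is covered, the second statistician works from the same SAP, and a check of derived values does not test how a coefficient's sign is read.
- **The reach is narrow.** One of the two measures of one secondary outcome is affected. This stands in full.

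A reader might infer that the EQ-5D-5L pain effect *will* be reported with the wrong sign. The documents do not support that. A reversal needs both steps: the item modelled in its listed order, and the result read by this sentence instead of by the response labels. Nor do they support the view that reverse coding is obligatory. Aligning the two scales is a choice of presentation, and a clear statement of direction is enough.

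**Conclusion.** The point holds as an internal inconsistency. On the level order given in SAP 6.1.2 and HEAP 4.3, the direction stated in SAP 6.2.2 is backwards. It wrongly gives EQ-5D-5L pain the same polarity as OMAS pain, and no reverse coding is specified to justify it.

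The consequence is conditional: the direction of the EQ-5D-5L pain effect at 2, 4 and 6 months could be misread, and could appear to contradict OMAS pain. The magnitude on the log-odds scale and the p-value do not change. OMAS pain, the primary outcome, the EQ-5D utility score and the sample size are untouched. The ordinal model itself is not in question.

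The conclusion assumes that the levels are numbered 1 to 5 in the order listed, and that the companion document, which could not be seen, does not already define a reversed variable. If it does, the SAP should say so. If it gives the listed order, the two documents conflict and the SAP sentence still needs correcting. The severity is minor to moderate.

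**What to change.** 1. In SAP 6.2.2, replace the direction sentence with: EQ-5D-5L pain runs from 1 = no pain to 5 = extreme pain; pain increases as the score increases. Alternatively, keep the present direction and state explicitly that the item is reverse-coded, for baseline and follow-up alike.
2. For each pain scale, state which direction of the odds ratio means less pain. If the item stays in its listed order, add that its odds ratio runs opposite to that for OMAS pain.
3. Check the Data Definitions and Tables document, the table shells and the analysis code for the same direction. If a reversed variable is created, keep it separate from the raw response used in the utility mapping.

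The cost is one or two sentences and a coding check. No data collection, sample size or model changes.

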## 6.3 Missing Data

Missing data will be minimised by careful data management. Missing data will be described with reasons given where available; the number and percentage of individuals in the missing category will be presented by treatment arm. All data collected on data collection forms will be used, since only essential data items will be collected. No data will be considered spurious in the analysis since all data will be checked and cleaned before analysis.

The primary analysis method proposed is reasonably robust to missing at random (MAR) data (18), but this assumption will be investigated by using a pattern mixture model, such as the Stata 'rctmiss' command. The missing data will be assumed to have the same distribution as the observed data, differing by a sensitivity parameter delta. The delta parameter will be the mean shifted value between observed and missing data, measuring the departure from MAR up to one standard deviation from the observed data value. This missing data sensitivity analysis can be used to explore the impact of any potential differential differences in the amount of missing data in the allocated treatment arms.

#### 6.4 Pre-specified Subgroup Analysis

Subgroup analysis will be conducted on fracture management (surgical vs non-surgical). The purpose of subgroup analyses is to investigate if the estimated treatment effects are relatively consistent across subgroup and for this extent will be viewed as exploratory.

The analysis population will be divided into their respective subgroup, and if there are too few participants in one subgroup (<=15) or one treatment arm of a subgroup (<=5), the analysis of that subgroup is likely to be biased due to small number of samples. In that case, that subgroup will be combined with other subgroups with more participants or the subgroup analysis will not be conducted.

Linear regression will be performed for each subgroup analysis. The model will include a treatment-subgroup interaction term to capture the effect of subgroups. The estimated treatment difference and confidence intervals will be reported and presented in forest plots. The results will be presented in forest plots with 95% confidence interval.

## 6.5 Supplementary/ Additional Analyses and Outcomes

The primary analysis ignores the potential clustering effect on outcomes of patients treated by the same therapist. The intra-cluster correlation coefficient (ICC) will be presented to indicate if the assumption of ignoring the therapist effect is fair for the primary analysis. We plan to test this assumption and perform a sensitivity analysis; this will be done by modelling the clustering therapist effect in the intervention arm as a random effect, and by treating the control arm as a single cluster. We will also explore, through the use of forest plots, the consistency of the therapist effect. (19, 20)

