#### 3.2 Randomization and Blinding

The randomization will be on a 1:1 basis to supervised versus self-directed rehabilitation, using a validated computer randomization program managed through a secure (encrypted) web-based service by the Oxford Clinical Trials Research Unit (OCTRU). Randomization will use a minimisation algorithm to ensure balanced allocation across the two treatment groups, stratified by centre and initial fracture management (surgical vs non-surgical). The first few participants will be randomised by simple randomization to seed the minimisation algorithm and a probabilistic element introduced to the algorithm to ensure the unpredictability of intervention allocation.

Full details of the randomization are available in AFTER\_RandomizationAndBlindingPlan\_V1.0\_27Jul2022, stored in the confidential statistical section of the Trial Master File (TMF).

Due to the nature of the intervention, it is not possible to blind participants or those delivering the intervention. The local research team at recruiting centres will also not be blinded to the treatment allocation.

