## 3.3 Sample Size

292 (146 per arm) participants providing primary outcome data at 6 months are required to detect a difference of 8 points on the OMAS score with an estimated standard deviation of 21 with 90% power and 5% (2-sided) significance. The minimum clinically important difference for the OMAS selected in surgical trials has usually been 10 points but for this trial of physiotherapy we have chosen a smaller difference of 8 points, which is likely to be clinically important and was supported by our patient advisory group. The chosen standard deviation of 21 is based on the AIM trial (6) (SD 21.7) and the feasibility study data (SD 20.5 based on 32 participants having reached the 6 month time-point). This equates to a standardised effect size of 0.38, a small to moderate effect. In the AFTER feasibility study there was 11% loss to follow-up (those not providing the primary outcome data). In order to allow for potential loss to follow-up of participants in the definitive trial we have inflated the sample size by 15% to aim for a minimum of 344 participants (172 per arm).

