#### 3.8 Statistical Analysis Outline

The primary analysis population will be the intention-to-treat population (ITT), that is participants will be analysed in the group in which they were randomised regardless of what treatment they received. The analyses will be repeated for the per protocol (PP) population. The per protocol population will exclude participants who did not receive the allocated treatment and participants with major protocol deviations, this will be finalised using blinded data prior to

the final datalock. Standard descriptive statistics will be used to describe the demographics between the treatment groups reporting means and standard deviations or medians and interquartile ranges as appropriate for continuous variables and numbers and percentages for binary and categorical variables. Standard statistical summaries and graphical plots will be presented for the primary outcome measure and all secondary outcome measures.

The OMAS score at 6 months is the primary outcome in this study and will be compared between treatment groups as the dependent variable in a mixed-effects linear regression model including outcome information at intermediate time-points. This model will adjust for stratification factors (initial fracture management; operative or non-operative) and baseline OMAS score. A random effect will be included to account for heterogeneity due to recruitment centres. The treatment effect will be based on adjusted mean differences at 6 months and will be reported together with their 95% confidence intervals.

We will also undertake a Complier Average Causal Effect (CACE) analysis which essentially compares the "compliers" in each group. The CACE analysis will be undertaken using the definition of full compliance in the intervention group – defined as receiving a minimum of 4 physiotherapy sessions. Partial compliance is receiving at least one physiotherapy session (i.e. starting the treatment), which will be used in the per-protocol analysis. This will provide supporting evidence to any findings from the principal analysis. Subgroup analysis by surgical vs non-surgical treatment of the fracture will be undertaken, using a treatment by subgroup interaction term and will be presented using forest plots.

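### SAP section 6.5 does not say whether the single control cluster enters the therapist random effect; if it does, the clustering check becomes badly conservative

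*SAP*

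**What the plan says.** Section 6.5 acknowledges that the primary analysis takes no account of patients sharing a therapist. It plans to report the ICC and to run one sensitivity analysis, described as "modelling the clustering therapist effect in the intervention arm as a random effect, and by treating the control arm as a single cluster". It gives no model equation and no choice between a random intercept and a random coefficient. It does not say whether the control cluster belongs to the random term.

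The quantity at issue is fixed in section 3.8: "The treatment effect will be based on adjusted mean differences at 6 months and will be reported together with their 95% confidence intervals". The design values are in section 3.3: "292 (146 per arm) participants providing primary outcome data at 6 months", "required to detect a difference of 8 points on the OMAS score with an estimated standard deviation of 21 with 90% power".

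**The concern.** The sentence in 6.5 holds two instructions, and the second is either idle or harmful, depending on how the first is coded.

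- **Random effect multiplied by the supervised-arm indicator.** Self-directed participants carry no therapist effect, so the way they are grouped has no influence.
- **One therapist identifier for all controls, random intercept on therapist.** The control arm receives its own random draw with the therapist variance. That draw coincides exactly with the arm contrast. The test then asks whether the control mean looks like one more draw from the spread of therapist means, not whether the two arm means are equal. Self-directed participants share no treating therapist, so nothing in the design corresponds to this variance.

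This is the only model planned to test the assumption that therapist clustering can be ignored. Under the second coding, a real benefit could look fragile to clustering purely because of the coding. Section 7 also asks an independent statistician to repeat the SAP's analyses for OMAS. Two competent people could follow this sentence and obtain standard errors that differ about twofold.

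**Working it through.** **Inputs from the SAP.** Difference 8 points, SD 21 (variance 441), two-sided 5%, 146 analysed per arm (3.3); 1:1 allocation (3.2).

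**Assumptions, not in the SAP.** Number of therapists K = 20 to 40 (3.1 gives only a minimum of 20 hospitals); therapist ICC 0 to 0.10; one 6-month comparison without covariates or repeated measures; Wald test at 1.96.

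**The plan's own figure.** n per arm = 2 × (21/8)² × (1.960 + 1.282)² = 144.8, so 145. The t-based calculation gives 90.0% power at 146 per arm, hence 292. Then 292/0.85 = 343.5, so 344. The sample size reproduces.

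**Variance of the treatment difference.** Write σu² = ICC × 441 and σe² = 441 − σu².

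- (a) Control cluster in the random intercept: σu²(1 + 1/K) + 2σe²/146
- (b) Random effect in the supervised arm only: σu²/K + σe²/146 + 441/146

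Example, ICC 0.05 and K = 30: σu² = 22.05, σe² = 418.95.

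- (a) SE = √(22.05 + 0.735 + 5.739) = √28.524 = 5.34; power = Φ(8/5.34 − 1.96) = 32%.
- (b) SE = √(0.735 + 2.870 + 3.021) = √6.625 = 2.57; power = Φ(8/2.57 − 1.96) = 87.5%.

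Without clustering, SE = √(2 × 441/146) = 2.46.

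**Over the ICC range.** Formula columns are for K = 20 with the variances known. Simulated columns use 20,000 trials per setting with the variances estimated, for K = 20 / 30 / 40.

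| ICC | (a) SE | (a) power, formula | (a) power, simulated | (b) SE | (b) power, formula | (b) power, simulated |
|---|---|---|---|---|---|---|
| 0 | 2.46 | 90.2% | 67.3 / 63.4 / 61.6% | 2.46 | 90.2% | 89.6 / 89.5 / 89.9% |
| 0.01 | 3.26 | 69.0% | 60.6 / 58.3 / 56.8% | 2.50 | 89.3% | 88.4 / 89.3 / 89.4% |
| 0.02 | 3.90 | 53.7% | 54.6 / 52.7 / 52.4% | 2.53 | 88.4% | 88.2 / 88.7 / 89.5% |
| 0.03 | 4.44 | 43.6% | 48.0 / 48.1 / 48.0% | 2.57 | 87.5% | 87.5 / 88.8 / 88.8% |
| 0.05 | 5.38 | 31.9% | 36.4 / 37.4 / 37.9% | 2.64 | 85.7% | 85.9 / 87.8 / 88.6% |
| 0.10 | 7.19 | 19.8% | 16.9 / 18.1 / 19.4% | 2.82 | 81.0% | 82.6 / 85.4 / 87.7% |

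At a true ICC of 0, power under (a) still falls, because the therapist variance is estimated above zero in nearly half of the trials. Over ICC 0.01 to 0.10, rejection under no effect is 0.7% to 2.8% for (a) and about 5% for (b).

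A second simulation used REML fits, unequal caseloads and 30 therapists. It gave (a) against (b) of 56% and 88% at ICC 0.02, 42% and 86% at 0.05, and 22% and 82% at 0.10.

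**The floor.** As participants and therapists increase without limit, variance (a) tends to σu², not to zero. At ICC 0.05, σu = 4.70, so an observed 8-point difference gives at most z = 8/4.70 = 1.70. With the variance known, 8 points cannot reach 1.96 once ICC exceeds (8/1.96)²/441 = 0.038.

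**Does the control label matter under (b)?** Mixed-model fits to four simulated data sets gave identical estimates and SEs whether controls formed one cluster or each stood alone. The random intercept with one control cluster gave the same estimate but a larger SE: for an estimate of 10.574, 4.679 against 2.560.

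**The case against.** The strongest reply is that 6.5 places the random effect in the intervention arm. On the natural reading that is already a partially nested model, in which the single-cluster label is harmless. One of the references cited there has a title about trials with clustering in one arm, which fits this reading. Nothing in 6.5 mentions a random intercept for controls. This stands: a reader might infer that the SAP prescribes the damaging model, and the text does not support that.

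A reader might also infer that the analysis simply loses half its power. The documents do not support that either, since they give no ICC and no number of therapists. By formula, power falls from 90% to 45% at an ICC of about 0.03. Over ICC 0.01 to 0.10 the relative loss under the adverse coding runs from about a quarter to four fifths. At ICC 0.02 or below, a true 8-point effect would still be significant more often than not.

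Further, 6.5 sets no rule that the primary result fails if this analysis loses significance. The calculation is also simpler than the planned model: covariates, centre and repeated measures would shift the percentages. They would not remove the floor, because the control cluster would still coincide with the arm.

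What the reply does not supply is a reason to keep the clause. Under the favourable reading it has no effect, and under the other it does damage.

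**Conclusion.** The point holds as an ambiguity with a potentially large effect on one sensitivity analysis; the SAP does not prescribe a wrong model. If the control cluster enters a therapist random intercept, simulated power for an 8-point difference is about 52% to 61% at ICC 0.01 to 0.02, 36% to 42% at 0.05 and 17% to 22% at 0.10, with type I error of about 1% to 3%. If the random effect is confined to the supervised arm, power is about 81% to 89% and type I error about 5%. These figures rest on the assumed ICC and therapist numbers and on a single-time-point comparison. That the full therapist variance enters the contrast under the adverse coding is algebra and does not depend on those values. The primary analysis, its sample size and its 90% power are not affected.

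**What to change.** In section 6.5, replace the closing clause about the control arm with a partially nested specification, for example: *The therapist random effect will enter only through the supervised-arm indicator (a random coefficient on that indicator, with no therapist random intercept for self-directed participants); all other terms are as in the primary model.* Arm-specific residual variance could be added but is optional; the problem described here does not depend on it.

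The cost is one sentence of SAP text and one line of model code. No new data are needed, because therapist identity is already required for this analysis. The change should be made before the outcome data are seen by arm, so that the coding is not chosen afterwards.
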